8.8 Records

8.8.1 Records Retention

The investigator must retain all study records and source documents for the maximum period required by applicable regulations and guidelines, or institution procedures, or for the period specified by the Sponsor, whichever is longer. The investigator must contact the Sponsor prior to destroying any records associated with the study.

The Sponsor will notify the investigator when the study records are no longer needed.

If the investigator withdraws from the study (eg, relocation, retirement), the records shall be transferred to a mutually agreed upon designee (eg, another investigator, EC). Notice of such transfer will be given in writing to the Sponsor.

8.8.2 Case Report Forms

An investigator is required to prepare and maintain adequate and accurate case histories designed to record all observations and other data pertinent to the investigation on each individual treated or entered as a control in the investigation. Data that are derived from source documents and reported on the CRF must be consistent with the source documents or the discrepancies must be explained. Additional clinical information may be collected and analyzed in an effort to enhance understanding of product safety. CRFs may be requested for AEs and/or laboratory abnormalities that are reported or identified during the course of the study.

Electronic CRFs will be prepared for all data collection fields except for fields specific to SAEs and pregnancy, which will be reported on the paper or electronic SAE form and Pregnancy Surveillance form, respectively. Spaces may be left blank only in those circumstances permitted by study-specific CRF completion guidelines provided by the Sponsor.

The confidentiality of records that could identify subjects must be protected, respecting the privacy and confidentiality rules in accordance with the applicable regulatory requirement(s).

The investigator will maintain a signature sheet to document signatures and initials of all persons authorized to make entries and/or corrections on CRFs.

The completed CRF, including any paper or electronic SAE/pregnancy CRFs, must be promptly reviewed, signed, and dated by the investigator or qualified physician who is a sub-investigator and who is delegated this task on the Delegation of Authority Form. For electronic CRFs, review and approval/signature is completed electronically through the Sponsor electronic data capture tool. The investigator must retain a copy of the CRFs including records of the changes and corrections.

Each individual electronically signing electronic CRFs must meet Sponsor training requirements and must only access the Sponsor electronic data capture tool using the unique user account provided by Sponsor. User accounts are not to be shared or reassigned to other individuals.

8.8.3 Subject identification – Personal Data protection

All records identifying the subject must be kept confidential and, to the extent permitted by the applicable laws and/or regulations, not be made publicly available. The name of the patient will not be asked for nor recorded at the Data Center. A sequential identification number will be automatically attributed to each patient registered in the study. This number will identify the patient and must be included on all case report forms. In order to avoid identification errors, date of birth will also be reported on the case report forms.

Any and all patient information or documentation pertaining to a clinical trial, to the extent permitting, through a “key” kept anywhere, regardless of whether such key is supplied along with the information or documentation or not, must be considered as containing sensitive personal data of the patient, and is therefore subjected to the provisions of applicable data protection (“privacy”) regulations. Breach of such regulations may result in administrative or even criminal sanctions.

Particularly, an information sheet prepared according to such regulations and a form to evidence the consent of patients to the processing of such data must therefore accompany the informed consent administered to the patient. Such information must (i) identify the roles of the holder and processor (“responsible”, appointed by the holder) of the patient personal data (also if not directly identifying the patient), as well as the purposes of the personal data collection and processing (medical treatment and related/unrelated scientific research), (ii) adequately describe the flows of communication involving them, particularly if third parties should become involved, and (iii) seek the patient’s prior and specific consent to such processing.

Patient information or documentation may be considered “anonymous”, and as such not subject to privacy regulations, only when no key whatsoever, permitting the identification of the patient, is any longer available.

Particular attention should therefore be paid (and information/consent materials adapted accordingly) whenever patient data are supplied to third parties and may be autonomously processed, or biological samples/materials are taken and kept for future research purposes, associated or not with the pathology considered in the study.

9. ETHICAL CONSIDERATION

Primary investigator will ensure that this study will be conducted in agreement with either the Declaration of Helsinki (Tokyo, Venice, Hong Kong and Somerset West amendments) or the laws and regulations of the country, whichever provides the greatest protection of the patient.

The protocol will be written, and the study will be conducted according to the ICH Guideline for Good Clinical Practice. The protocol and its annexes will be subject to review and approval by the competent Independent Ethics Committee(s) (“IEC”) at each study center.

9.1 Informed consent

The Investigator has both ethical and legal responsibility to ensure that each subject being considered for inclusion in this study is given a full explanation of the study. Written informed consent will be obtained from all subjects (or their guardians or legal representatives) before any study-related procedures (including any pre-treatment procedures, such as pre-procedure sedation) are performed or given. Written informed consent will be documented on an informed consent form (ICF) approved by the same Independent Reviewing Authority (IRA) responsible for approval of this protocol. The ICF will conform to ICH GCP guidelines and to the institutional requirements for

informed consent and applicable regulations. The ICF will be reviewed with the prospective study subject or his or her legal representative, and the Investigator or qualified designee will be available to answer questions regarding procedures, risks, and alternatives. The subject will receive a copy of the signed ICF. The original signed and dated ICF will be kept in the site's regulatory file. Documentation of the subject's informed consent for and participation in this study will be noted in the subject's medical record.

10. STATISTICAL ANALYSIS

<https://www.sample-size.net/> (Kohn MA, Senyak J. Sample Size Calculators [website]. UCSF CTSI. 29 April 2021) has been used to calculate the sample size. We consider the expected rate of patients with ALC less than 500 cells/mL being 40% one month after RT end, according to previous works showing this rate being 30% at 3 months in head and neck cancer series treated with RT (18), and the estimated 3-year recurrence-free survival being 36% in patients with ALC less than 500 cells/mL and 63% in patients with ALC greater than 500 cells/mL, so HR=0.45 (JAMA Otolaryngol Head Neck Surg. 2019;145(5):413-421. doi:10.1001/jamaoto.2019.0034).

All statistical analyses will be performed using SPSS version 23.0 (SPSS, Chicago, IL).

10.1 Sample size calculations

To test the Hazard Ratio between Group0 (patients with ALC less than 500 cells/mL) and Group1 (patients with ALC greater than 500 cells/mL) of 0.3 with type I error rate of 5% and power of 80%, we need a minimum of 23 total events which in our hypothesis of median survival time in Group 0 equal to 18 months, 5% censoring rate and whole duration of the study of 4 years correspond to 42 patients, 17 in the Group0 and 25 in the Group1..

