4.3 Duration of study

The duration of the treatment is limited by the completion of adjuvant radiotherapy.

This study will take 24 months to conclude the enrollment of 42 patients.

Follow up of the patients will be carried out according to clinical practice, with periodic visits and

instrumental assessments. Patients' follow-up will continue for 24 months after the end of radiation and patients still alive will be considered as censored.

Therefore, the whole duration of the study (enrollment + follow up) will be 48 months.

First results will be evaluated in an interim-analysis (primary and secondary objectives of before-after RT change in immune populations) at 24 months.

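### Section 10 derives a hazard ratio of 0.45, but section 10.1 sizes the study for 0.3 without a reason; with 23 events, power at 0.45 is about 47%, not 80%.

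*Combined protocol and SAP*

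**What the plan says.** Section 10 supplies the only documented effect size. For the group below the cut-off it cites "the estimated 3-year recurrence-free survival being 36% in patients with ALC less than 500 cells/mL". Its figure for the group above the cut-off, with the hazard ratio it draws from the pair, is "63% in patients with ALC greater than 500 cells/mL, so HR=0.45". It also expects 40% of patients to be below the cut-off one month after radiotherapy.

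Section 10.1 sizes the comparison of the same two groups for a hazard ratio "of 0.3 with type I error rate of 5% and power of 80%, we need a minimum of 23 total events". It converts events to patients using a "median survival time in Group 0 equal to 18 months". The remaining inputs and the result are given as "5% censoring rate and whole duration of the study of 4 years correspond to 42 patients", split 17 and 25.

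Section 4.3 sets the follow-up: "This study will take 24 months to conclude the enrollment of 42 patients", "follow-up will continue for 24 months after the end of radiation", and "the whole duration of the study (enrollment + follow up) will be 48 months".

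**The concern.** Two adjacent paragraphs give different effect sizes for one comparison, and the power statement uses the more favourable one. The gap is not rounding. With 36% event-free at 3 years in Group 0, a hazard ratio of 0.3 implies 74% in Group 1, against the cited 63%. It is not a misprint for 0.45 either, because 23 events is the correct answer for 0.3.

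Section 10.1 is the only sample-size justification for the primary outcome. If the documented effect is the true one, the study is about as likely to miss it as to find it. A reader of the plan would believe the chance of finding it is 80%, and could then take a null result as evidence that lymphopenia after radiotherapy does not matter in this disease.

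**Working it through.** **Inputs.** Section 10: 3-year rates 36% and 63%; 40% of patients in Group 0. Section 10.1: hazard ratio 0.3, type I error 5%, power 80%, 23 events, 17 and 25 patients, 18-month Group 0 median, 5% censoring. Section 4.3: 24 months of enrolment, 24 months of follow-up after radiation, 48 months overall. The plan does not say whether the test is one- or two-sided.

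**Hazard ratio in section 10.** Under proportional hazards, ln 0.63 / ln 0.36 = 0.452, so 0.45 is reproduced. Conversely, 0.36^0.30 = 0.736, the 74% quoted above.

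**The plan's 23 events.** Schoenfeld's formula with a 40:60 split is d = (1.960 + 0.842)² / (0.24 × (ln HR)²).
- HR 0.30, two-sided 5%: 22.6, so 23. This matches the plan.
- HR 0.30, one-sided 5%: 17.8, so 18. Two-sided is therefore inferred.
- HR 0.45, two-sided 5%: 51.3, so 52.

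**Power with 23 events.** Power = Φ(√(0.24 × 23) × |ln HR| − 1.960).
- HR 0.30: 80.8%.
- HR 0.45: 46.7% (46.8% with the exact 17:25 split).
- HR 0.45, one-sided 5%: 59%.
- Log-rank simulation stopped at 23 events: about 85% at HR 0.30 and 53% at HR 0.45.

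**Events from 42 patients.** Assume exponential survival and read the 5% censoring as per year. Per group, expected events = n × λ/(λ + c) × (1 − exp(−(λ + c)F)), with λ₀ = ln 2/18, λ₁ = HR × λ₀ and c = −ln(0.95)/12 per month. F is follow-up in months. In the staggered case (entry over 24 months, cut-off at month 48), the result is averaged over F from 24 to 48.

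| Follow-up | HR 0.30: events, power | HR 0.45: events, power |
|---|---|---|
| 24 months each | 9.8 + 5.8 = 15.6, 64% | 9.8 + 8.1 = 17.9, 38% |
| Staggered, cut-off at month 48 | 11.9 + 7.9 = 19.7, 75% | 11.9 + 10.7 = 22.6, 46% |
| 48 months each | 13.3 + 9.7 = 23.1, 81% | 13.3 + 12.9 = 26.3, 52% |

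(Group figures are rounded, so a sum can differ by 0.1.) The 48-month row at HR 0.30 needs 41.9 patients for 23 events, which reproduces the plan's 42. The first two rows are the ones section 4.3 allows.

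**Sensitivity.** Reading the 5% as total drop-out (events × 0.95, no other loss) gives 64% and 75% at HR 0.30, and 38% and 46% at HR 0.45, for the same two rows. Simulated log-rank power for those rows is 67% and 76% at HR 0.30, and 41% and 49% at HR 0.45.

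**The 18-month median.** Under a constant hazard it implies exp(−ln 2 × 36/18) = 25% event-free at 3 years, not 36%. Taking λ₀ from the 36% instead gives 12.4 to 16.2 events and 55% to 66% power at HR 0.30, and 14.3 to 18.6 events and 32% to 39% at HR 0.45, for the same two rows.

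**The case against.** The strongest objection is that 0.45 has no special standing. It comes from an oropharyngeal cancer series (reference 18), and section 1.3 says that no study has examined lymphopenia in cutaneous squamous cell carcinoma. The sponsor may plan for a different effect. That stands, but it makes 0.45 uncertain without supporting 0.3. The fault is that the design value has no justification.

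The event counts for 42 patients depend on assumptions that the hazard-ratio mismatch does not need. That is also correct, and they should be labelled as such. If the 5% is total drop-out, 23 events at HR 0.30 need about 45 months of follow-up each instead of 48, which is still well beyond 24. Section 6 collects survival status for at least 24 months, so stopping everyone at 24 is the low end; the staggered case covers the longer reading. Replacing the 18-month median with the cited 36% lowers power further.

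The 47% is an approximation, and simulation gives about 53%. Neither is near 80%.

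Finally, radiotherapy follows clinical practice and no treatment depends on this calculation, so one could rate the point lower. Even so, the plan claims 80% power for a formal test of its primary outcome, and that claim should match its stated basis.

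**Conclusion.** The concern holds and must be fixed. The 80% power applies to a hazard ratio of about 0.30 with 23 events, while the only effect the plan documents is 0.45. At 0.45, power with 23 events is about 47% by Schoenfeld's formula, and 80% needs 52 events. These figures rest on a two-sided 5% test, which the plan's own 23 events imply, and on the 40:60 split; a one-sided test does not rescue the claim.

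Separately, under the follow-up in section 4.3, 42 patients are expected to give about 16 to 20 events and 64% to 75% power at 0.30, or about 18 to 23 events and 38% to 46% power at 0.45. These ranges also assume exponential survival, the unsourced 18-month median and 5% censoring per year.

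**What to change.** Keep 42 patients and restate sections 10 and 10.1 so that they say:

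1. The test is two-sided, if that is what was intended.
2. The 80% power applies only to a hazard ratio of about 0.30 and only if 23 events occur. Under the calculation's assumptions, 42 patients reach that number with about 48 months of follow-up each, whereas section 4.3 gives about 16 to 20 events and 64% to 75% power at 0.30.
3. The value 0.30 does not come from the 36% and 63% figures, and why it was chosen.
4. At 0.45, power is about 47% with 23 events, and about 38% to 46% for 42 patients under section 4.3.
5. The assumptions behind the event counts: the survival model, the meaning of the 5% censoring, and the source of the 18-month median, with a note on how it fits the 36% at 3 years.

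Re-sizing for 0.45 would need 52 events and is a much larger change. The restatement alters no patient number, visit or follow-up; its cost is the rewording and a lower stated power.

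### The 18-month Group 0 median behind the 42 patients has no stated source and, under the constant hazard that reproduces 42, does not match the 36% 3-year recurrence-free survival assumed in section 10

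*Combined protocol and SAP*

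**What the plan says.** Section 10 lists the planning assumptions. The share of patients with "ALC less than 500 cells/mL being 40% one month after RT end" is taken from earlier work, and outcome is set by "the estimated 3-year recurrence-free survival being 36% in patients with ALC less than 500 cells/mL" against 63% in the other group. From these two rates it draws a hazard ratio of 0.45, citing a published series.

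Section 10.1 then sizes the study on a hazard ratio of 0.3, with 5% type I error and 80% power. It states "we need a minimum of 23 total events" and, as the study team's own hypothesis, a "median survival time in Group 0 equal to 18 months", together with "5% censoring rate and whole duration of the study of 4 years". These are said to "correspond to 42 patients, 17 in the Group0 and 25 in the Group1". No source or derivation is given for the 18 months, and no survival model is named.

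Section 4.3 plans 24 months of accrual, then follow-up for 24 months after the end of radiotherapy, 48 months in all.

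**The concern.** Sections 10 and 10.1 describe the same group of patients, those with low ALC after radiotherapy, by two survival figures. If the hazard is constant, the two figures give different event rates, and the calculation uses the one that yields more events. Power in a time-to-event comparison depends on the number of events, so a median that is too short makes 42 patients look sufficient when they may not be. At stake is whether the 80% power in section 10.1 can be supported from the plan's own assumptions.

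**Working it through.** **Inputs.** From section 10.1: hazard ratio 0.3, 5% type I error, 80% power, Group 0 median 18 months, 5% censoring, 4 years, 17 + 25 patients. From section 10: 40% low ALC; 36% and 63% at 3 years. From section 4.3: 24 months of accrual, 24 months of follow-up after radiotherapy. Assumed, because the plan does not say: two-sided test, exponential survival, and 5% loss per year (c = 0.05/12 per month). An overall 5% loss is also shown.

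**1. Reproduce the plan.** Schoenfeld events = (1.960 + 0.842)² / [0.4 × 0.6 × (ln 0.3)²] = 7.849 / (0.24 × 1.450) = 22.6, rounded up to 23.

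Probability of an event within T months = λ/(λ + c) × [1 − exp(−(λ + c)T)]. With λ₀ = ln 2/18 = 0.0385, λ₁ = 0.3 × λ₀ = 0.0116 and T = 48 for everyone, this is 0.786 in Group 0 and 0.389 in Group 1. Then N = 22.56 / (0.4 × 0.786 + 0.6 × 0.389) = 41.2, split 16.5/24.7 and rounded up to 17 + 25 = 42. The plan's figures are reproduced. Expected events are 17 × 0.786 + 25 × 0.389 = 23.1.

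Power = Φ(|ln HR| × √[d × (17/42) × (25/42)] − 1.96). For d = 23.1 and HR 0.3: Φ(2.84 − 1.96) = 81%.

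**2. Compare the two survival figures under that model.**
- 18-month median: 0.5^(36/18) = 25% at 3 years, and 0.25^0.3 = 66% in Group 1.
- 36% at 3 years: median = 36 × ln 2 / (−ln 0.36) = 24.4 months.

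**3. Change only the median** (HR 0.3, 48 months each).
- 24.4 months, 5% per year: event probabilities 0.689 and 0.306, 19.4 events, 74% power. For 23 events, about 23 / (19.4/42) = 50 patients would be needed.
- 24.4 months, 5% overall: 20.0 events, 75% power.
- 24.4 months, no loss: 21.0 events, so the loss assumption does not close the gap.

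**4. Drop the constant hazard.** A Weibull curve through 50% at 18 months and 36% at 36 months has shape ln(ln 0.36/ln 0.5)/ln 2 = 0.56. With HR 0.3, 48 months each and 5% per year it gives 18.4 events and 72% power.

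**5. Use both cited rates.** HR = ln 0.63/ln 0.36 = 0.452. With 48 months each and 5% per year: event probabilities 0.689 and 0.421, 22.2 events, power Φ(1.84 − 1.96) = 45%. With follow-up spread evenly over 24–48 months: 18.7 events, 39%. At HR 0.45, 80% power needs about 52 events.

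**6. Follow-up alone** (18-month median and HR 0.3 unchanged).

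| Follow-up | Events | Power |
|---|---|---|
| 48 months each | 23.1 | 81% |
| 24–48 months, even accrual | 19.8 | 75% |
| 24 months each | 15.6 | 65% |

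**The case against.** Four arguments can be made for the plan.

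- **The 36% is not given as the origin of the 18 months.** A reader might infer that it is, because the sections are adjacent and concern the same group. The documents do not support this: section 10 uses the two rates only to reach a hazard ratio of 0.45, and section 10.1 offers 18 months as a hypothesis. The cited source is in oropharyngeal cancer, and this study enrols cSCC at head and neck and other sites, so a different median may be defensible. This stands, but the plan does not make that case, and the 36% is the only sourced survival figure for Group 0.
- **The figures conflict only under a constant hazard.** Also true, and section 10.1 names no model. A falling hazard can fit both. The shortfall remains, however (step 4).
- **The 23 events and 80% power follow from the stated inputs.** They do (step 1). A reader might infer an arithmetic error in section 10.1; there is none. The issue is an input.
- **The cited rates nearly deliver 23 events.** With 36% and 63% together, 42 patients give about 22. So it is too strong to say that the plan's source yields too few events because of the median. On that route power fails because the hazard ratio is 0.45 and not 0.3.

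A reader might also take 74% as the study's true power. It is not: a 24.4-month median with hazard ratio 0.3 puts Group 1 at 0.36^0.3 = 74% at 3 years, against the cited 63%, further off than the 66% implied now. Nor should the lower power figures that come from shorter follow-up be charged to the median; step 6 shows that follow-up lowers events with 18 months unchanged.

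**Conclusion.** The point holds as a failure to source and reconcile an input. Taken alone, and at hazard ratio 0.3 with 48 months for everyone, aligning the median with the 36% costs about 3 to 4 events and 6 to 7 percentage points of power (81% to 74% with 5% loss per year; 82% to 75% with 5% overall). It is the smaller of three problems in the calculation. Sizing on 0.3 when section 10 derives 0.45 matters most: power is about 45% on the cited rates, or about 39% with 24–48 months of follow-up. Giving every patient 48 months, against section 4.3, is the other.

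These results rest on a two-sided 5% test, the 17/25 split, proportional hazards and, except in step 4, exponential survival; the 24–48-month case also assumes even accrual.

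**What to change.** In section 10.1, either justify the 18-month median and say why it departs from the 36% in section 10, or replace it with 24.4 months. Do not change the median in isolation. In the same revision:

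- settle the hazard ratio (0.3 or 0.45), so that the rates implied for both groups agree with section 10 or the departure is explained;
- set the follow-up used in the calculation to match section 4.3;
- name the survival model, and say whether the 5% censoring is per year or overall;
- restate expected events and power for 42 patients under the reconciled inputs.

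The cost is a rewording of the sample-size section and a less favourable stated power. Keeping 42 patients requires no change to recruitment or procedures.

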4.2 Follow up

After the completion of the study analysis at day 28 (+/- 3 days) after radiotherapy, the patients will remain in follow up.

The follow up of will be carried out according to clinical practice, with periodic visits and instrumental assessments, which should performed with the following timepoints:

- Clinical examination every 3 months for the first year, then every 6 months
- Radiological imaging 3 months after RT completion, then every 6 months

Disease free survival of the patients, overall survival, possible side effects and other treatments performed in adjuvant or palliative settings will be collected.

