6. ASSESSMENT OF EFFICACY

Blood samples will be collected at two time point to assess immune-modulating effects of adjuvant radiotherapy.

The following blood cells will be assessed at baseline (day -1) before adjuvant RT and at day 28 (+/- 3) after RT completion:

- circulating T cells CD3+CD8+ and CD3+CD4+
- absolute lymphocyte (ALC) count and neutrophil counts (ANC) and neutrophil/lymphocyte ratio (NLR)
- Treg lymphocytes, defined as CD4+CD25+FOXP3+ or CD4+CD25hi+CD39+ cells.
- Naïve/Memory T lymphocytes CD4+ and CD8+ (defined as CD45RA/CD45RO)
- myeloid-derived suppressor cells, defined as cells expressing Lin-neg (CD3, CD14, CD15, CD19, CD56) /HLA-DR-/CD33+/CD11b+ in either a “lymphocyte” (small FSCxSSC) gate, or in a “monocyte” (larger FSCxSSC) gate, and as HLA-DR+/lo CD14+ cells in a large gate.
- Plasmacytoid Dendritic Cells (CD303+CD123+)
- NK cells dim (CD3-CD16+CD56+) and bright (CD3-CD16-CD56++);
- NKT cells (CD3+CD56+);
- Myeloid Dendritic cells (CD1c+ and CD141+);
- Monocyte subsets (classical CD14+CD16-, intermediate CD14+CD16+, non classical CD14+/-CD16+);
- B lymphocytes (CD19+);
- Analysis of plasma cytokines (TNFalpha, TGFbeta, IL-6, IL-10) by ELISA;
- IFN signature: real-time PCR on mRNA from PBMCs

A centralized evaluation of all blood and tissue samples collected will be performed at the Department of Molecular and Translational Medicine, Oncological-Immunological Experimental Section, University of Brescia.

Follow up of all subjects enrolled will be conducted according to clinical practice, with periodic visits and instrumental assessments. Survival status of the patients and possible other treatments performed will be collected for at least 24 months.

Plasma and mRNAs will be stored at the Department of Molecular and Translational Medicine, Oncological-Immunological Experimental Section, University of Brescia. All samples will be identified by a specific numerical code.

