10.2 Statistical plan

Disease-free survival and overall survival in treated patients will be analyzed with a Cox proportional hazards regression, first univariable and then multivariable.

Change between T0 (28 days after RT) and T1 (24 months) in secondary endpoints, all recorded as continuous variables, will be modelled using linear mixed models (or GEE), accounting for within patient repetition. The interaction between time and ALC status will be the effect of interest. All models will adjust for potentially confounding clinical variables.

.11.SCHEDULE OF EVALUATION

Evaluation	Screening	TREATMENT PERIOD			Follow up at 24 months
		Day -1	RT treatment (period 0)	Day +28 (from the end of RT)	
Informed consent	X				
Inclusion/exclusion criteria	X				
Medical history	X				
ECOG PS Status	X				
Vital signs	X				
Evaluation of high-risk factors for recurrence	X				
RT treatment			X		
RT characteristics (site-volume-dose)			X	X	
Immune markers *		X		X	
Molecular profile		X			
Outcomes: DFS and OS					X

*circulating T cells CD3+CD8+ and CD3+CD4+

absolute lymphocyte (ALC) count and neutrophil counts (ANC) and neutrophil/lymphocyte ratio (NLR)

Treg lymphocytes, defined as CD4+CD25+FOXP3+ or CD4+CD25hi+CD39+ cells.

Naïve/Memory T lymphocytes CD4+ and CD8+ (defined as CD45RA/CD45RO)

myeloid-derived suppressor cells, defined as cells expressing Lin-neg (CD3, CD14, CD15, CD19, CD56) /HLA-DR-/CD33+/CD11b+ in either a “lymphocyte” (small FSCxSSC) gate, or in a “monocyte” (larger FSCxSSC) gate, and as HLA-DR+/lo CD14+ cells in a large gate.

Plasmacytoid Dendritic Cells (CD303+CD123+)

NK cells dim (CD3-CD16+CD56+) and bright (CD3-CD16-CD56++);

NKT cells (CD3+CD56+);

Myeloid Dendritic cells (CD1c+ and CD141+);

Monocytes subsets (classical CD14+CD16-, intermediate CD14+CD16+, non classical CD14+/-CD16+);

B lymphocytes (CD19);

Analyses of plasma cytokines (TNFalpha, TGFbeta, IL-6, IL-10) by ELISA;

IFN signature: real-time PCR on mRNA from PBMCs

Any other treatment performed by the patient in case of progression will be collected and reported in the CRF.

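### Section 10.1 appears to use the 4-year study length as each patient's time at risk; with 24 months of follow-up after RT, 42 patients give about 16 events, not 23

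*Combined protocol and SAP*

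**What the plan says.** Section 10.1 sizes the primary DFS comparison between patients with post-RT ALC below 500 (Group 0) and above 500 (Group 1). It assumes a hazard ratio of 0.3, 5% type I error and 80% power, which requires 23 events. With a Group 0 median of 18 months it then states that "5% censoring rate and whole duration of the study of 4 years correspond to 42 patients", split 17 and 25.

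The length of follow-up is described in four other places:

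- Section 4.3 allows 24 months for enrolment and says that "follow-up will continue for 24 months after the end of radiation", after which patients still alive are censored. It concludes that "the whole duration of the study (enrollment + follow up) will be 48 months".
- The schedule in section 11 has one outcome column for DFS and OS, headed "Follow up at 24 months".
- Section 4.2 sets visits as "Clinical examination every 3 months for the first year, then every 6 months", with no end date.
- Section 6 says: "Survival status of the patients and possible other treatments performed will be collected for at least 24 months".

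**The concern.** The 4 years in section 4.3 are calendar time from first enrolment to study end. They are not the time for which a patient is observed. Expected events depend on the latter. If 48 months per patient were used in the conversion from events to patients, 42 is too few to give 23 events within the follow-up that section 4.3 describes.

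The 5% censoring figure does not repair this. It can stand for drop-out, but not for patients who are still event-free when follow-up ends, and with 24 months each those would be the majority.

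This is the only sizing for the primary comparison. If the study is analysed with about 16 events while claiming 80% power, a null result could be read as evidence that lymphopenia has no prognostic effect.

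**Working it through.** **Inputs.** From section 10.1: hazard ratio 0.3, alpha 5% (sidedness not stated; two-sided reproduces 23), power 80%, Group 0 median 18 months, 5% censoring, 17 and 25 patients. From section 10: 40% expected with ALC below 500. From section 4.3: 24 months of enrolment and 24 months of follow-up after RT. Assumptions: exponential survival, and uniform accrual where entry is staggered.

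**1. Required events (Schoenfeld).** d = (1.960 + 0.842)² / [(17/42)(25/42)(ln 0.3)²] = 7.85 / (0.2409 × 1.4496) = 22.5, rounded up to 23. The plan's figure is reproduced.

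**2. How 42 arises.** The hazards are ln 2/1.5 = 0.462 per year in Group 0 and 0.3 × 0.462 = 0.139 per year in Group 1. With a censoring hazard of 0.05 per year and time T at risk, the event probability is λ/(λ + 0.05) × [1 − exp(−(λ + 0.05)T)]. At T = 4 years for every patient this gives 0.786 and 0.389. Then N = 23 / (0.4 × 0.786 + 0.6 × 0.389) = 41.97, which is the stated 42. Staggered entry over 24 months with everyone followed to closure 24 months after the last entry gives N of about 46 without losses and 49 to 50 with 5% per year, so it does not reproduce 42.

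**3. Time at risk needed.** For 17 + 25 patients to give 23 events, each must be at risk for 41.2 months with no loss, 45.3 months with a flat 5% loss, or 47.8 months with 5% loss per year.

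**4. Events under 24 months each, no loss.** Monthly hazards are 0.0385 and 0.0116.

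- Group 0: 17 × [1 − exp(−24 × 0.0385)] = 17 × 0.603 = 10.25
- Group 1: 25 × [1 − exp(−24 × 0.0116)] = 25 × 0.242 = 6.05
- Total: 16.3

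Power = Φ(√(16.3 × 0.2409) × |ln 0.3| − 1.96) = Φ(0.43) = 66.5%. The share expected to be event-free at 24 months is 1 − 16.3/42 = 61%.

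**5. All scenarios: expected events (power by the same formula).**

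| Time at risk | No loss | Flat 5% loss | 5% loss per year |
|---|---|---|---|
| 48 months each | 25.0 (84%) | 23.7 (82%) | 23.1 (81%) |
| 24 months each | 16.3 (67%) | 15.5 (64%) | 15.6 (65%) |
| To closure when the last patient reaches 24 months (uniform 24–48) | 21.1 (77%) | 20.0 (75%) | 19.8 (75%) |
| To closure at month 48, assuming 6 weeks to end of RT (uniform 22.5–46.5) | 20.5 (76%) | 19.5 (74%) | 19.3 (74%) |

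With 24 months each, 23 expected events would take about 60 to 63 patients. If time at risk starts at the day-28 ALC measurement, about 23 months remain and 15 to 16 events are expected.

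**6. Simulation check.** With no loss or 5% drop-out, log-rank simulation gives 69 to 70% power for 24 months each and 78 to 80% for follow-up to closure. Power is a little lower if losses are 5% per year. The simulated chance of reaching 23 events, with no loss or a flat 5% loss, is 1 to 2% with 24 months each and 16 to 31% with follow-up to closure.

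**7. Side note on the median.** Section 10 cites "the estimated 3-year recurrence-free survival being 36% in patients with ALC less than 500 cells/mL". Under exponential survival that implies a median of 36 × ln 2 / (−ln 0.36) = 24.4 months, not 18. Keeping the hazard ratio at 0.3, that median gives 13.0 events (57%) with 24 months each and 17.3 (69%) for uniform 24–48, before losses. The conclusion does not rest on this.

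**The case against.** - **Longer follow-up may be intended.** Section 6 sets a minimum and section 4.2 sets no end date, so patients may be followed to closure. Simulated power is then close to the claimed 80%, and the shortfall is about 2 to 4 events. This stands as a limit on the size of the problem. It does not remove it: section 4.3 and the schedule point to 24 months, the choice moves power by about 10 percentage points, and neither reading is expected to give 23 events.
- **The mechanism is inferred.** Section 10.1 never says that 4 years is individual time at risk. That is so, although the match at 41.97 makes the inference strong. The shortfall does not depend on it, because it follows from the planned follow-up and the plan's own survival assumptions.
- **This is an inconsistency, not a miscalculation.** It is fair to say that 23 and 42 both reproduce from the inputs as entered. The fault is that the duration entered does not agree with section 4.3.
- **The 24.4-month scenario is a hybrid.** It joins a rate from an oropharyngeal series to a hazard ratio of 0.3 that the series does not support, and 18 months is labelled a hypothesis. This is accepted. At most a reason for the 18 months is missing.

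**Conclusion.** The concern holds. The 23 events and 80% power in section 10.1 do not match the follow-up planned elsewhere in the protocol. Under the 24-month rule of section 4.3, 42 patients are expected to give 15.5 to 16.3 events. Power is then 64 to 67% by the plan's own type of calculation, or about 69 to 70% by simulation. With follow-up of everyone to a common closure, the expected count is 19.3 to 21.1 and the loss of power is small.

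These figures assume exponential survival, a two-sided 5% test, the plan's hazard ratio of 0.3 and its 18-month median, and a 17:25 split. How the 5% censoring is read changes the 24-month result by less than one event. That section 10 derives a hazard ratio of 0.45 while section 10.1 uses 0.3 is a separate matter; the calculation here takes the more favourable value.

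**What to change.** 1. **Adopt one follow-up rule** and use it in sections 4.2, 4.3, 6 and the schedule in section 11. Keep the 24-month minimum after RT for every patient, and go on collecting DFS and OS for earlier-enrolled patients until study closure (about month 48, or when the last patient reaches 24 months after RT).
2. **Restate section 10.1** for that rule, giving expected events and power with administrative censoring included, in place of 23 events and 80%. On the current assumptions this is about 19 to 21 events. If the sponsor prefers to stop at 24 months per patient, section 10.1 should report about 16 events and the corresponding power.
3. **Say whether the 5% censoring is a total or a yearly rate**, and that it covers drop-out only. A sentence giving the reason for the 18-month median would help.

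The cost is wording, plus outcome data from routine visits for patients enrolled early. No patients are added. If the last patient enrols at month 24, keeping 24 months after RT moves closure past month 48 by the time from enrolment to the end of RT (about 6 weeks if a 30-fraction course is assumed). Section 4.3 already implies this.
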